212 Any history of malignancy with the following exceptions:

- resolved non-melanoma skin cancers > 5 years prior to screening.
- resolved cervical carcinoma > 5 years prior to screening.
- resolved breast ductal carcinoma in situ > 5 years of screening.

Prior/Concomitant Therapy

- 213 Currently receiving or had treatment with: cyclophosphamide, chlorambucil, nitrogen mustard, or any other alkylating agent within 6 months prior to screening or sirolimus within 4 weeks prior to screening.
- 237 Currently receiving or had treatment with a Janus kinase (JAK) inhibitor **or** **tyrosine kinase (TYK) inhibitor** within less than 5 drug half-lives prior to screening.
- 215 Currently receiving or had treatment with an immune checkpoint inhibitor (eg, PD-1 inhibitor, PD-L1 inhibitor, CTLA-4 inhibitor).

Note: Abatacept is not considered a CTLA-4 inhibitor and is referred to below.

- 216 Currently receiving or had treatment within 12 months prior to screening with T-cell depleting agents (eg, antithymocyte globulin, Campath).
- 217 Currently receiving or had treatment with an IL-2 based therapy (eg, Proleukin).
- 238 Current or previous treatment with a biologic agent with immunosuppressive/immunomodulatory activity as follows: rituximab within 6 months prior to screening; abatacept, belimumab, and anifrolumab within the past 3 months prior to screening; other biologics within < 5 drug half-lives prior to screening.
- 219 Subjects who have received intraarticular, intralesional, or intramuscular corticosteroids within 2 weeks prior to screening or intravenous corticosteroids within 6 weeks prior to screening.
- 220 Subjects who have received live vaccines within 5 weeks prior to screening, or plan to receive live vaccines during the treatment period and up to 6 weeks after the end of treatment period in the study.

Prior/Concurrent Clinical Study Experience

- 221 Currently receiving treatment in another investigational device or drug study.
- 222 Ending a treatment with an investigational drug or investigational device less than 3 months or 5 half-lives from the last dose of the investigational drug (whichever is longer) at screening.

Diagnostic Assessments

- 236 Presence of laboratory abnormalities at screening including the following:
- Aspartate aminotransferase (AST) or alanine aminotransferase (ALT) > 2 x upper limit of normal (ULN).
 - Serum total bilirubin (TBL) \geq 1.5 mg/dL (\geq 26 μ mol/L) except for Gilbert's Syndrome.

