- Wilson's disease and hemochromatosis
- Nonalcoholic fatty liver disease including steatohepatitis
- Non-hepatic causes (eg, rhabdomyolysis, hemolysis)

If investigational product(s) is/are withheld, the subject is to be followed for possible drug induced liver injury (DILI) according to recommendations in the last section of this appendix.

Rechallenge may be considered if an alternative cause for impaired liver tests (ALT, AST, ALP) and/or elevated TBL, is discovered and the laboratory abnormalities resolve to normal or baseline (see next section in this appendix).

Table 11-3. Conditions for Withholding and/or Permanent Discontinuation of Amgen Investigational Product and Other Protocol-required Therapies Due to Potential Hepatotoxicity

Analyte	Temporary Withholding	Permanent Discontinuation
TBL	> 3x ULN at any time	> 2x ULN OR
INR	--	> 1.5x (for subjects not on anticoagulation therapy) AND
AST/ALT	> 8x ULN at any time > 5x ULN but < 8x ULN for \geq 2 weeks > 5x ULN but < 8x ULN and unable to adhere to enhanced monitoring schedule > 3x ULN with clinical signs or symptoms that are consistent with hepatitis (such as right upper quadrant pain/tenderness, fever, nausea, vomiting, and jaundice)	> 3x ULN (when baseline was < ULN), in the presence of no important alternative causes for elevated AST/ALT and/or TBL values
ALP	OR > 8x ULN at any time	--

ALP = alkaline phosphatase; ALT = alanine aminotransferase; AST = aspartate aminotransferase; INR = international normalized ratio; TBL = total bilirubin; ULN = upper limit of normal

Criteria for Rechallenge of Amgen Investigational Product and Other Protocol-required Therapies After Potential Hepatotoxicity

The decision to rechallenge the subject is to be discussed and agreed upon unanimously by the subject, investigator, and Amgen.

If signs or symptoms recur with rechallenge, then efavaleukin alfa is to be permanently discontinued. Subjects who clearly meet the criteria for permanent discontinuation (as described in Table 11-3) are never to be rechallenged.

Drug-induced Liver Injury Reporting and Additional Assessments

Reporting

To facilitate appropriate monitoring for signals of DILI, cases of concurrent AST or ALT and TBL and/or INR elevation, according to the criteria specified in the above, require the following:

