- The event is to be reported to Amgen as a serious adverse event immediately and no later than 24 hours of discovery or notification of the event (ie, before additional etiologic investigations have been concluded)
- The appropriate **case report form (CRF)** (eg, Events eCRF) that captures information necessary to facilitate the evaluation of treatment-emergent liver abnormalities is to be completed and sent to Amgen

Other events of hepatotoxicity and potential DILI are to be reported as serious adverse events if they meet the criteria for a serious adverse event defined in Section 11.4.

Additional Clinical Assessments and Observation

All subjects in whom investigational product(s) or protocol-required therapies is/are withheld (either permanently or conditionally) due to potential DILI as specified in **Table 11-3** or who experience AST or ALT elevations $> 3 \times$ upper limit of normal (ULN) or 2-fold increases above baseline values for subjects with elevated values before drug are to undergo a period of “close observation” until abnormalities return to normal or to the subject’s baseline levels.

Assessments that are to be performed during this period include:

- Repeat AST, ALT, ALP, bilirubin (BIL) (total and direct), and INR within 24 hours
- In cases of TBL $> 2 \times$ ULN or INR > 1.5 , retesting of liver tests, BIL (total and direct), and INR is to be performed every 24 hours until laboratory abnormalities improve

Testing frequency of the above laboratory tests may decrease if the abnormalities stabilize or the investigational product(s) or protocol-required therapies has/have been discontinued AND the subject is asymptomatic.

Initiate investigation of alternative causes for elevated AST or ALT and/or elevated TBL.

The following are to be considered depending on the clinical situation:

- Complete blood count with differential to assess for eosinophilia
- Serum total immunoglobulin (Ig)G, anti-nuclear antibody anti-smooth muscle antibody, and liver kidney microsomal antibody-1 to assess for autoimmune hepatitis
- Serum acetaminophen (paracetamol) levels

- A more detailed history of:
 - Prior and/or concurrent diseases or illness
 - Exposure to environmental and/or industrial chemical agents
 - Symptoms (if applicable) including right upper quadrant pain, hypersensitivity-type reactions, fatigue, nausea, vomiting and fever
 - Prior and/or concurrent use of alcohol, recreational drugs and special diets

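### Table 11-3's permanent stop for combined transaminase and bilirubin or INR elevation does not cover eligible subjects with baseline AST/ALT of 1 to 2x ULN (low priority)

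*Protocol*

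**What the plan says.** Protocol Section 6.2.3 sends liver stopping rules to Appendix 7 (Section 11.7). Those rules apply only where no other cause of the liver changes has been found.

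- **Permanent discontinuation (Table 11-3).** Bilirubin above 2x ULN, or INR above 1.5 in subjects not on anticoagulants, together with AST/ALT "> 3x ULN (when baseline was < ULN), in the presence of no important alternative causes for elevated AST/ALT and/or TBL values". Subjects who clearly meet these criteria may never be rechallenged.
- **Temporary withholding (Table 11-3), with no baseline condition.** Bilirubin above 3x ULN; AST/ALT above 8x ULN; AST/ALT between 5x and 8x ULN for 2 weeks or more, or without feasible enhanced monitoring; AST/ALT above 3x ULN with "clinical signs or symptoms that are consistent with hepatitis (such as right upper quadrant pain/tenderness, fever, nausea, vomiting, and jaundice"; or ALP above 8x ULN.
- **Rechallenge after a hold.** "Rechallenge may be considered if an alternative cause for impaired liver tests (ALT, AST, ALP) and/or elevated TBL, is discovered", provided the tests return to normal or baseline, and the decision must be "agreed upon unanimously by the subject, investigator, and Amgen".
- **Close observation.** AST or ALT above 3x ULN, or "2-fold increases above baseline values for subjects with elevated values before drug". With bilirubin above 2x ULN or INR above 1.5, retesting "is to be performed every 24 hours until laboratory abnormalities improve".
- **24-hour serious adverse event report.** Paired transaminase and bilirubin or INR elevation, "according to the criteria specified in the above".

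Eligibility (Section 5.2, criterion 236) excludes "Aspartate aminotransferase (AST) or alanine aminotransferase (ALT) > 2 x upper limit of normal (ULN" at screening.

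**The concern.** The eligibility limit and the stopping rule use different baselines. Criterion 236 admits AST/ALT up to 2x ULN, but the only permanent stop that pairs transaminases with bilirubin or INR is limited to baselines below ULN. A baseline exactly at ULN is also outside it. Appendix 7 gives subjects with raised baselines their own trigger for close observation, but none for permanent discontinuation.

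The issue is patient safety. Two subjects with the same on-study liver tests and no other explanation can receive different mandatory dosing actions, and the subject who entered with mildly raised enzymes gets the weaker one. Detection is not the problem. The missing piece is the required dosing action.

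**Working it through.** The plan gives no figure to reproduce, so the check is to follow the rule as written.

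**Notation.** B = baseline AST/ALT, A = on-study AST/ALT, T = bilirubin (all in multiples of ULN); I = INR. No alternative cause and no anticoagulation are assumed.

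- Permanent stop: (T > 2 or I > 1.5) and A > 3 and B < 1.
- Hold: T > 3, or A > 8, or 5 < A < 8 (for at least 2 weeks or not monitorable), or A > 3 with hepatitis signs or symptoms, or ALP > 8.

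**Raised baseline.** If B is 1 to 2, the permanent stop is never met. Given A > 3 and (T > 2 or I > 1.5), no Table 11-3 action is required only when every hold condition also fails. That needs no signs or symptoms, A above 3 to 5 (or 5-8 for under 2 weeks with monitoring), T no more than 3, and ALP no more than 8. Any other pattern gives a hold.

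**Illustrative cases** (ALP 1x ULN, monitored, under 2 weeks):

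| A | T | I | B = 0.9 | B = 1.0, 1.5 or 2.0, no symptoms | Same B, with jaundice |
|---|---|---|---|---|---|
| 3.1 | 2.1 | 1.0 | permanent stop | no action | hold |
| 3.5 | 2.5 | 1.0 | permanent stop | no action | hold |
| 4 | 2.5 | 1.0 | permanent stop | no action | hold |
| 4.9 | 3.0 | 1.0 | permanent stop | no action | hold |
| 7 | 2.5 | 1.0 | permanent stop | no action | hold |
| 4 | 1.0 | 1.6 | permanent stop | no action | hold |
| 4 | 3.5 | 1.0 | permanent stop | hold | hold |
| 9 | 2.5 | 1.0 | permanent stop | hold | hold |

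The cases were chosen to map the region, so the counts are not frequencies. A second grid of 4 AST/ALT values by 3 bilirubin/INR pairs gives the permanent stop in 12 of 12 combinations at B = 0.8, and in 0 of 12 at each of B = 1.0, 1.2, 1.5 and 2.0.

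**Effect of a baseline-relative clause.** Suppose a stop is required at A > 3 and A at least 2B, with the same bilirubin or INR condition. The threshold is the larger of 3 and 2B: 3.0 at B = 1.0 or 1.5, 3.5 at B = 1.75, and 4.0 at B = 2.0. All eight cases then stop at B = 1.0 and 1.5. At B = 2.0, six stop. The first two do not, because 3.1/2.0 = 1.55 and 3.5/2.0 = 1.75 are below 2-fold. A separate hold is needed for them.

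**The case against.** The strongest reply is that these subjects are far from unprotected, and much of it stands.

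- **Automatic holds.** Bilirubin above 3x ULN, AST/ALT above 8x ULN, or jaundice triggers a Table 11-3 hold whatever the baseline. A reader might infer that these subjects have no rule at all, or only ever a judgement-dependent hold. Table 11-3 does not support either reading. Because rechallenge after a hold needs another cause, resolution and unanimous agreement, the difference from a permanent stop is small once a hold applies.
- **The 5-8x band partly closes itself.** Dosing is every 2 weeks, so an elevation that persists to the next nominal dose has normally reached the 2-week hold. Only a dose given early within the 5-day window would escape.
- **Discretion and oversight.** Section 7 lets the investigator or sponsor stop product at any time, and Section 7.1 lists adverse events and sponsor decision among the reasons. Under Appendix 3 an unblinded DMC reviews safety about every 12 weeks. These are real safeguards, but none is a required action for the individual subject.
- **The serious-event route.** If the 24-hour report covers these subjects, Section 6.2.2.1 requires product to be withheld for a possibly related serious event. With no alternative cause, relatedness would be hard to deny. On that reading a hold would normally follow. The other reading is that the cross-reference carries the baseline limit with it, and the text does not settle which is meant. Even the first reading gives a hold until grade 2 or lower, not a permanent stop.
- **Deliberate choice.** The protocol plainly considered raised baselines, since it assigns them close observation. A reader might infer a departure from the liver-injury guidance that the appendix cites. That cannot be checked from these documents and is not claimed.

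**Conclusion.** The point holds in a limited form. Eligible subjects with baseline AST/ALT of 1 to 2x ULN have no permanent stop equivalent to the one for baselines below ULN, and no matching rechallenge ban. Within the narrow region set out above, Table 11-3 requires no dosing action for them. What remains there is close observation with daily retesting, discretion to stop, DMC review, and a Section 6.2.2.1 hold if the event is judged possibly related and serious and/or clinically significant grade 3 or higher.

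This rests on two readings. First, Table 11-3 is treated as mandatory: the appendix title speaks of suggested actions, but its text calls them stopping and withholding rules. Second, the table as extracted is taken to be complete; its permanent-discontinuation cells read coherently, with no sign of a lost row.

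The documents do not say how many subjects had a raised baseline or met the paired criteria. A reader might infer that subjects here were dosed through such an event, but nothing in the documents shows that. SAP Section 3.1 records that the study was terminated for futility and product discontinued, so no protocol change can affect a subject in this trial. Priority is low.

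**What to change.** For any later efavaleukin protocol:

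1. In the AST/ALT permanent-discontinuation cell add: *or, when baseline was >= ULN, > 3x ULN and >= 2x baseline*, under the same bilirubin/INR and no-alternative-cause conditions. The 2x-baseline figure is adapted from the close-observation trigger. The documents do not state it as a stopping threshold, so the sponsor should confirm it.
2. Require a temporary hold when AST/ALT is above 3x ULN with bilirubin above 2x ULN or INR above 1.5 but the rise is less than 2x baseline.
3. State that the 24-hour serious adverse event report applies whatever the baseline.

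For this study's report, add one listing of subjects with AST/ALT above 3x ULN plus bilirubin above 2x ULN (or INR above 1.5 where measured), split by baseline AST/ALT (below ULN, at or above ULN), with the dosing action taken. SAP Section 9.6.1 names drug related hepatic disorder as an event of interest and Section 9.6.2 plans laboratory shift tables. Neither describes a display that pairs these tests within a subject or shows the dosing action. INR will be sparse, because coagulation is scheduled only at screening.

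The cost is a few lines of protocol text, a few more mandatory stops or holds, and one listing from data already collected.

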## List of Abbreviations

Abbreviation	Explanation
ACR	American College of Rheumatology
AE	adverse event
ALP	alkaline phosphatase
ALT	alanine aminotransferase
ANC	absolute neutrophil count
ANCOVA	analysis of covariance
Anti-dsDNA	anti-double stranded DNA
AST	aspartate aminotransferase
BHM	Bayesian Hierarchical Model
BICLA	BILAG based Combined Lupus Assessment
BILAG	British Isles Lupus Assessment Group
CLASI	Cutaneous Lupus Erythematosus Area and Severity Index
Clinical SLEDAI-2K	SLEDAI-2K assessment score without the inclusion of points attributable to any urine or laboratory results including immunologic parameters.
CNS	central nervous system
COVID-19	Coronavirus Disease 2019
CTCAE	Common Terminology Criteria for Adverse Events
DMC	data monitoring committee
ECG	electrocardiogram
eCRF	Electronic Case Report Form
EOS	end of study
ET	early termination
FAS	Full Analysis Set
GLM	Generalized linear model
hSLEDAI	Hybrid Systemic Lupus Erythematosus Disease Activity Index
IA	interim analysis
IBG	Independent Biostatistics Group
Ig	immunoglobulin
IL-2	interleukin 2
IP	Investigational product

IPD	Important protocol deviation
IRT	interactive response technology
LLDAS	Lupus Low Disease Activity State
NSAID	non-steroidal anti-inflammatory drugs
OCS	oral corticosteroids
PD	pharmacodynamic
PGA	Physician Global Assessment
PK	pharmacokinetic
PROMIS	Patient-Reported Outcome Measurement Information System
Q2W	every 2 weeks
RAR	Response Adaptive Randomization
SAP	statistical analysis plan
SF36v2	Medical Outcomes Short Form 36 version 2 questionnaire
SLE	systemic lupus erythematosus
SLEDAI-2K	Systemic Lupus Erythematosus Disease Activity Index 2000
SLICC	Systemic Lupus International Collaborating Clinics
SOC	standard of care
SRI	Systemic Lupus Erythematosus Responder Index
Treg	regulatory T cells
VAS	visual analog scale

## 1. Introduction

The purpose of this Statistical Analysis Plan (SAP) is to provide details of the statistical analyses that have been outlined within the protocol amendment **3** for study 20200234, Efavaleukin Alfa dated **21 October 2022**. The scope of this plan **is reduced from those outlined in the protocol due to determination of futility at a preplanned interim analysis and subsequent study early termination.** It includes the final analysis that is planned and will be executed by the Amgen Global Biostatistical Science department unless otherwise specified.

## 2. Objectives, Endpoints and Hypotheses

### 2.1 Objectives and Endpoints/Estimands

[figure not shown]
Objectives	Endpoints
Primary	

Evaluate the efficacy of efavaleukin alfa at week 52, as measured by the SRI-4 response

	

SRI-4 response at week 52

Primary Estimand	
The primary estimand is the difference in SRI-4 response rates between each efavaleukin alfa dose group and placebo at week 52 for all subjects with SLE with inadequate response to SOC therapy who are randomized, regardless of investigational product compliance; subjects will be considered non-responders for using more than protocol-permitted therapies including: 

Subjects requiring a dose of systemic corticosteroids for SLE above their baseline dose after week 16

Subjects requiring either dose increases of the current immunosuppressants/immunomodulators or initiation of new immunosuppressant/immunomodulator(s)

	
Secondary	

Evaluate the efficacy of efavaleukin alfa at week 52, as measured by the BICLA index responses

	

BICLA response at week 52

Evaluate the efficacy of efavaleukin alfa at week 52, as measured by LLDAS response

	

LLDAS response at week 52

Evaluate the efficacy of efavaleukin alfa at week 52, as measured by OCS tapering

	

Reduction of OCS to <math>\leq 7.5</math> mg/day by week 44 and sustained through week 52 in subjects with a baseline OCS dose <math>\geq 10</math> mg/day

Evaluate the efficacy of efavaleukin alfa at week 24, as measured by SRI-4 response

	

SRI-4 response at week 24

Evaluate the efficacy of efavaleukin alfa at week 24, as measured by the BICLA index responses

	

BICLA response at week 24



Evaluate the efficacy of efavaleukin alfa at weeks 24 and 52, as measured by hSLEDAI

	

hSLEDAI response (i.e., reduction <math>\geq 4</math> points from baseline) at week 24

hSLEDAI response (i.e., reduction <math>\geq 4</math> points from baseline) at week 52

Evaluate the efficacy of efavaleukin alfa on joints and skin

	

Improvement from baseline in tender and swollen joint count <math>\geq 50\%</math> at weeks 8, 12, 24, 36, and 52 in subjects with <math>\geq 6</math> tender and swollen joints involving hands and wrists at baseline

Improvement from baseline in CLASI activity score <math>\geq 50\%</math> at week 8, 12, 24, 36, and 52 in subjects with a CLASI activity score <math>\geq 8</math> at baseline

Evaluate the efficacy of efavaleukin alfa using BILAG score

	

Annualized flare rate (as measured by BILAG score designation of “worse” or “new” resulting in a B score in <math>\geq 2</math> organs or an A score in <math>\geq 1</math> organ) over 52 weeks

Evaluate the efficacy of efavaleukin alfa using patient reported outcomes

	

Change from baseline in fatigue standardized score using the PROMIS Fatigue SF 7a at week 12, 24, 36, and 52

Change from baseline in the physical component score, mental component score and individual domains of the SF 36 v2 at week 12, 24, 36, and 52

Change from baseline in the domain scores on the Lupus QoL at weeks 12, 24, 36, and 52

Characterize the safety of efavaleukin alfa

	

Treatment-emergent adverse events

Serious adverse events

Clinically significant changes in laboratory values and vital signs

• Characterize the PK of efavaleukin alfa

	

• Trough and sparse postdose serum concentrations of efavaleukin alfa

---	---

BICLA = British Isles Lupus Assessment Group Based Composite Lupus Assessment; CLASI = Cutaneous Lupus Erythematosus Area and Severity Index ; hSLEDAI = Hybrid Systemic Lupus Erythematosus Disease Activity Index; IL-2 = interleukin-2; LLDAS = Lupus Low Disease Activity State; OCS = oral corticosteroid; PGA = Physician Global Assessment; [REDACTED]  
[REDACTED] PK = pharmacokinetic(s); PROMIS Fatigue SF7A = Patient-Reported Outcome Measurement Information System Fatigue Short Form 7a Instrument; QoL = quality of life; SLE= systemic lupus erythematosus; SF36v2 = Medical Outcomes Short Form 36 version 2 Questionnaire; SOC = standard of care; SRI-4 = Systemic Lupus Erythematosus Responder Index; [REDACTED]  
[REDACTED]

**Exploratory**

**2.2 Hypotheses and/or Estimations**

At least 1 efavaleukin alfa dose will have greater efficacy than placebo as measured by the SRI-4 response rate at week 52 in subjects with active SLE with inadequate response to SOC therapy who are randomized, regardless of investigational product compliance; subjects using more than protocol-permitted therapies will be considered as non-responders:

- Subjects requiring a dose of systemic corticosteroids for SLE above their baseline dose after week 16
- Subjects requiring either dose increases of the current immunosuppressants/immunomodulators or initiation of new immunosuppressant/immunomodulator(s).

**3. Study Overview**

**3.1 Study Design**

This is a Bayesian adaptive phase 2b, multi-center, double-blind, randomized, placebo-controlled dose ranging study in subjects with active SLE and inadequate response to SOC therapies, including OCS, immunosuppressants, and immunomodulators.

Previous biologic use is allowed with an adequate washout period.

The study design includes 3 active efavaleukin alfa treatment groups [REDACTED] every 2 weeks [Q2W], [REDACTED] Q2W, and [REDACTED] Q2W) and a placebo group, SRI-4 response at week 52 as the primary endpoint, and an approximate sample size of 320 subjects.

Subjects will be randomized to receive either placebo or 1 of 3 doses of efavaleukin alfa for a duration of 52 weeks. The randomization ratio will start as 1:1:1:1, and then may be adapted at planned interim analyses (IAs) based on the clinical efficacy, as measured by SRI-4 response, using Response Adaptive Randomization (RAR) for the purpose of

allocating more subjects to more efficacious doses and fewer subjects to less efficacious doses, with a fixed 25% of subjects allocated to placebo throughout the study. The RAR will be implemented with a computerized system that assigns a treatment to subjects without unblinding any study personnel or Amgen study team members, including the investigators or subjects, to the subject's randomized treatment assignment or the current allocation ratio.

Study duration for a single subject will be 56 weeks (including the safety follow-up period) plus the screening period. Treatment will be administered every 2 weeks with the final dose at week 50. All subjects will be followed for safety for 6 weeks after the last dose of investigational product.

Subjects will undergo a screening visit to confirm eligibility requirements. At day 1 (baseline), prior to randomization, disease activity (clinical hybrid SLEDAI score  $\geq 4$ ) and stability and compliance of OCS and other immunosuppressant/immunomodulator doses, must be present. The maximum time between screening and randomization is 33 days. Subjects who do not meet all the eligibility requirements prior to randomization on day 1 will be considered screen failures. Subjects may be allowed to rescreen three times.

Immunosuppressant/immunomodulator dose(s) should remain stable through week 52. For OCS, initiation or temporary increases in OCS are allowed between weeks 0 to 10, provided that return to baseline dose occurs within the subsequent 2 weeks. OCS may be tapered after week 12 at the investigator's discretion but should not be changed during the last 8 weeks (week 44 to 52) of the 52-week treatment period.

Subjects who meet the criteria listed below will be allowed to continue the study but will be considered as experiencing treatment failure for the primary efficacy endpoint analyses:

- Subjects requiring a dose of systemic corticosteroids for SLE above their baseline dose after week 16
- Subjects requiring either dose increases of the current immunosuppressants/immunomodulators or initiation of new immunosuppressant/ immunomodulator(s)

IAs will be conducted to allow for adaption of the randomization ratio for newly enrolled subjects to the 3 efavaleukin alfa treatment groups, holding the allocation to placebo

constant at 25%, and assessing efficacy for early futility or administrative success decisions:

- The study team, investigators, and subjects will remain blinded to the results of the IAs unless futility is determined.
- The first IA will be executed after the first 40 subjects are randomized and have had the opportunity to complete the week 24 assessment. Subsequent IAs are scheduled after every additional 32 subjects are randomized and have had the opportunity to complete the week 24 assessment until full enrollment or until futility is determined for all doses at an IA. The last IA will occur when all 320 subjects are randomized and have had the opportunity to complete the week 24 assessment. This IA will be referred to as the 'all-subjects-week-24 IA'. Analyses planned at each IA are listed in [Table 3-1](#).
- Efficacy analyses will be performed at the IAs to assess the likelihood of each efavaleukin alfa treatment group being superior to placebo by a clinically meaningful difference.
  - From the second IA until before the last IA, if this likelihood is unacceptably low for all dose levels, the trial is recommended to stop for futility.
  - At the 'all-subjects-week-24 IA', if this likelihood is sufficiently high with at least one efavaleukin alfa dose level, this IA will trigger an administrative success signal. This would not alter the ongoing or planned activities of this phase 2b study, but downstream planning for subsequent trials (e.g., a phase 3 study) may commence.
- **Based on the Data Monitoring Committee's recommendation following review of the results from the 3rd IA and subsequent decision by the Data Access Plan Team, the study was terminated due to futility and further enrollment in the study was stopped. Previously enrolled subjects were discontinued from IP and terminated the study after being followed for an additional 6 weeks following last dose of IP. The remaining planned IAs, including the 4th to the last IA ('all-subjects-week-24-IA') were not conducted.**

